### **5.8 Premature Termination or Suspension of Study**

This study may be temporarily suspended or prematurely terminated if there is sufficient reasonable cause. If the study is prematurely terminated or suspended, the PI will promptly inform the IRB and will provide the reason(s) for the termination or suspension.

Circumstances that may warrant termination or suspension include, but are not limited to:

- Insufficient compliance to protocol requirements
- Technological malfunction
- Insufficient data quality
- Unanticipated loss of human resources such as study staff or clinical dermatologists.

Study may resume once concerns about protocol compliance, technology function, data quality, and/or resources are addressed and satisfy the IRB.

## **6 Study Agent (Study drug, device, biologic, vaccine etc.) and/or Procedural Intervention**

### **6.1 Study Agent(s) and Control Description**

The Procedural Intervention is the telemedicine evaluation; the Control is the in-person dermatologist evaluation. The Procedural Intervention includes 3 components:

- 1) Clinical images (from 6 inches, 12 inches, and 24 inches from the lesion) captured and uploaded to the subject's EPIC EMR medical chart as a research note or captured by the Barco Demetra and uploaded to its associated software
- 2) Close up clinical and dermoscopic imaging of the lesion(s) of concern with a dermoscopy camera (DermLite Cam, 3Gen, San Juan Capistrano, CA or Barco Demetra, Barco NV, Kortrijk, BE)
- 3) An electrical impedance spectroscopy measurement of said lesions using the Nevisense 3.0 device (Scibase, Sundbyberg Sweden)
- 4) Store-and-forward telemedicine evaluation of the imaging and Nevisense measurements by a team of 3 dermatologists.

The goal is to determine whether the lesion(s) of concern to the participant is a benign skin growth, or a possible skin cancer in need of a biopsy to definitively establish the diagnosis. The Nevisense 2.0 device is FDA cleared for use in dermatologists' offices. The Nevisense 2.0 device will not be used in this study. Rather, the updated, not yet approved Nevisense 3.0 device will be used. The 3.0 version consists of a software update and provides a simpler a workflow that no longer requires a reference measurement from the subject's normal skin, thus saving time. The 3.0 device has no change in the hardware.. Verbal FDA clearance occurred in January 2020 and formal FDA clearance is expected in April 2020. Regardless of approval, the proposed use of Nevisense 3.0 in a telemedicine setting for this study represents an off-label use of the device.

It measures electrical impedance of the lesion with single-use electrodes (i.e. changed between each participant). The device has a hardware probe that takes the measurement in <10 seconds and a software component that displays the data on the control unit screen.

Risks related to the device may be expected in <1.0% of cases. Most common to least common side effects include bleeding during measurement, pain, soreness, bruising, slight tingling at measurement site, headache, or itching at the measurement site. There may be unknown side effects. The DermLite Cam and Barco Demetra imaging devices pose non-significant risks to the participant. Capturing clinical and dermoscopic images with this device will take <1 minute per lesion.

### **6.1.1 Acquisition**

DermLite Cam will be purchased from 3Gen. The Nevisense 3.0 will be provided by SciBase. The disposable electrodes will be purchased from SciBase. The commitment letter from SciBase is found as Supplement I.

The Barco Demetra device has been approved by NYU MCIT for research use (see included email from [name], Lead IT Controls and Regulatory Compliance Analyst).

### **6.1.2 Formulation, Appearance, Packaging, and Labeling**

The Nevisense device is commercially available in the US. The Nevisense appears a control unit with a probe. The disposable electrodes are marked both on the package box and in each individual electrode packaging. The package insert is found as Supplement B. The product is available on the commercial market for human use in the form planned in this trial.

The DermLite Cam device appears as a single piece camera with a charging cable and USB computer cable. As part of the camera unit, an extensor arm exists to allow for the capture of standardized clinical images. The package insert is found as Supplement J.

The Barco Demetra digital dermatoscope appears as a two-piece device consisting of the Demetra Scope Head and Rechargeable grip/battery back with a battery charging station. The device also comes with a non-contact cone and user guide. The package insert is found as Supplement X.

### **6.1.3 Product Storage and Stability**

There is no particular storage needs for stability for either the Nevisense device or DermLite Cam. Both will remain locked in the DCSU when not in active use, accessible only to study personnel.

### **6.1.4 Device Specific Considerations**

Nevisense 3.0 will be used with the latest software upgrade as a one-time exposure of <8 seconds per lesion. Disposable electrodes that contact the participant are 5mm x 5mm in size.

According to the FDA PMA, current indications for Nevisense use are the following:

- primary skin lesions with a diameter between 2 mm and 20 mm;
- lesions that are accessible by the Nevisense probe;

- lesions where the skin is intact (i.e., non-ulcerated or non-bleeding lesions);
- lesions that do not contain a scar or fibrosis consistent with previous trauma;
- lesions not located in areas of psoriasis, eczema, acute sunburn or similar skin conditions;
- lesions not in hair-covered areas;
- lesions which do not contain foreign matter;
- lesions not on special anatomic sites (i.e., not for use on acral skin, genitalia, eyes, mucosal areas).

We will follow these indications except for prohibiting areas of psoriasis or eczema as the study personal taking the Nevisense measurements in this study will most often not be a physician and will not have the dermatological expertise to diagnose these conditions or similar conditions. Any potential risk from using this device in such skin conditions will be mitigated by the fact that other diagnostic tools will be used on every lesion of concern (clinical images and dermoscopic images) and the fact that each concerning lesion will be assessed by an in-person dermatologist, the current gold standard for diagnostic evaluation.

Additionally, lesions with crust, on a stalk, recurrent after biopsy or excision will not be included for Nevisense measurement as these lesion types were excluded from the pivotal studies for FDA PMA. . Crust (the medical term for a scab) is defined as dried serum or blood, typically overlying skin ulceration, or resulting from the rupture of vesicles or pustules.

The DermLite Cam will be used to acquire 3 images of <5 seconds per lesion (one clinical, one polarized dermoscopic, and one non-polarized dermoscopic). Images will be stored in a dedicated computer folder in the Dermatology Department server share using software (MoleCam, MoleMap, NZ) already in use by the telemedicine team in the NYU Department of Dermatology Pigmented Lesion Clinic. The telemedicine dermatology team will review the images using this dedicated software.

In addition to the DermLite Cam images, a study specific camera or EPIC HAIKU will be used to acquire 3 clinical images of <5 seconds per lesion (from 6 inches away, 12 inches away, and 18 inches away). Images will be stored in the patient's medical record in Epic, to which the teledermatology team has access. Clinical images taken through Epic Haiku or the study specific camera will not be stored elsewhere. Images taken with the study specific camera will be deleted from the camera once images are uploaded to EPIC.

The Barco Demetra device will be used to acquire 3 images of <5 seconds per lesion (one clinical, one polarized dermoscopic, and one non-polarized dermoscopic) as well as 3 additional clinical images of <5 seconds per lesion (from 6 inches away, 12 inches away, and 18 inches away). Images will be stored in the authenticated and data-encrypted Demetra Cloud accessible via the web by the telemedicine team in the NYU Department of Dermatology Pigmented Lesion Clinic. The telemedicine dermatology team will review the images using this dedicated cloud software. Clinical and dermoscopic images taken by the Barco Demetra device will not be stored elsewhere.

Lesions with bleeding or ulceration will only have a clinical image taken and not have a dermoscopic image taken.

The telemedicine dermatology team will consist of [name], [name], and [name], who are all pigmented lesion experts. They will be listed as co-investigators. They will submit independent, blinded to each other, diagnoses for each lesion on REDCap. If at least one teledermatologist believes the lesion to be a malignant diagnosis, the lesion will be recommended for biopsy. If the participant has not already had the lesion biopsied by the in-person recommendation, the participant will be told this concern for malignancy and telemedicine recommendation for biopsy.

## **6.2 Study Agent Accountability Procedures**

The two devices and photos will be used by study personnel. Nevisense measurements will be taken by all study team members that have completed the Nevisense training, as per page 4 of the device Instructions For Use (Supplement C). Most often, the individual obtaining Nevisense measurements will be non-physician study team members to simulate the eventual use in a pharmacy setting. Data acquired from the devices will be transferred to the participant source documents at the time of their visit. The results of the control evaluation will also be recorded at the time of the visit. At the end of each day, the data will be entered into the REDCap database case report forms and verified by a second study staff member. The devices will stay in a locked office in the DCSU when not in use. The images will be stored on an NYU server, behind institutional firewall, and backed up according to standard institutional schedules, minimizing the possibility of data loss.

## **7 Study Procedures and Schedule**

### **7.1 Study Procedures/Evaluations**

#### **7.1.1 Study Specific Procedures**

- Assessment of eligibility (number of lesions, location of lesions)
- Informed Consent
- Enrollment questionnaire (Supplement K)
- Nevisense EIS measurement
- Imaging of the lesion(s) of concern using the DermLite Cam and stored on MoleCam software and MoleCam drive behind NYU MCIT firewall OR using the Barco Demetra and stored on its associated cloud server
- Imaging of the lesion(s) of concern uploaded to EPIC EMR research note using study specific camera or EPIC HAIKU
- Numbering of skin lesions using Devon Skin Marker to verify same lesion evaluated across all assessments
- Administration of part 1 of study completion questionnaire (Supplement L)
- Skin lesion examination by in-person dermatologist
- Phone call to communicate telemedicine recommendation within 3 business days (phone script as Supplement M & N)
- Skin biopsy, if recommended by either the in-person dermatologist or the telemedicine evaluation
  - A skin biopsy is a small procedure that removes a sample of skin from the surface of the body. The method utilized will be either a shave or punch technique. The maximum size of a punch biopsy will be 6mm and these wounds are generally closed with absorbable sutures and do not require a return visit for suture removal. A skin biopsy takes <15 minutes including preparation time, administration of intradermal anesthesia using lidocaine 1% with epinephrine 1:100,000, removal of the skin sample, achievement of hemostasis, dressing the wound, and providing instructions for home care. Samples will be placed in formalin for routine processing.
- Administration of final study completion questionnaire (Supplement L).

#### **7.1.2 Standard of Care Study Procedures**

- Histopathological diagnosis of biopsied skin lesions
- Phone calls to discuss skin biopsy results and check on wound healing
- If necessary, suture removal visit is scheduled (if nylon sutures were placed during skin biopsy) and/or wound check visit.

### **7.2 Laboratory Procedures/Evaluations**

#### **7.2.1 Clinical Laboratory Evaluations**

- Routine dermatopathology examination of skin biopsy specimens

#### **7.2.2 Specimen Preparation, Handling, and Storage**

Skin biopsy specimens will be transferred on the day of removal to the NYU Dermatopathology Laboratory for processing and diagnosis, which is estimated to take 1-2 weeks. Biopsy samples will be labeled with participant identifying information including name and MRN.

### **7.3 Study Schedule**

As described below, the study schedule includes a variable number of visits that depend upon the outcome of the initial evaluation. Briefly, 3 outcomes are possible:

- 1) The lesion(s) is diagnosed as not suspicious for skin cancer by both the in-person dermatologist and telemedicine team, and no biopsy is recommended
- 2) The lesion(s) is diagnosed as not suspicious for skin cancer by the in-person dermatologist, but suspicious for skin cancer by the telemedicine team, and a biopsy is recommended when the telemedicine team results are communicated to the participant
- 3) The lesion(s) is diagnosed suspicious for skin cancer by the in-person dermatologist, and a biopsy is performed at the initial visit, or scheduled to be performed at a follow up visit. In this scenario, the recommendation of the telemedicine team will not be communicated to the participant since we do not yet know if a 'no biopsy' recommendation by the telemedicine team is a safe alternative to a 'biopsy' recommendation by the in-person dermatologist.

Based on the outcomes described above, the participant will have either 1 visit and 1 phone call (initial evaluation and follow-up phone call), or an additional visit for telemedicine recommended biopsy and an additional phone call with biopsy results.

### 7.3.1 Pre-Screening

#### Pre-Screening Visit (no time frame prior to enrollment)

- Participant reads general requirements for eligibility and calls to schedule an appointment at the DCSU if study requirements are met
- During the scheduling phone call, study staff determine if the prospective participant meets eligibility criteria (Supplement O & P)
- During the phone call, eligible participants have the option to view and discuss the consent form electronically. If they opt to do so, participants will be sent a consent form through RedCap, which they can view during the phone call and sign at any time prior to Visit 1. After signing the electronic consent form, participants also have the option to fill out the enrollment questionnaire electronically.

### 7.3.2 Enrollment/Baseline

#### Enrollment/Initial Visit (Visit 1, Day 1)

- Participant and lesion eligibility confirmed by study personnel
  - This is the formal study screening prior to official enrollment (i.e. signing informed consent)
- Participant given Key Information Sheet with an overview of the study (Supplement Q)
- Conduct informed consent procedure and obtain signed ICF, if not conducted electronically prior to visit
- Assign subject ID for participant
- Obtain demographic information, medical history, medication history as part of enrollment questionnaire (Supplement K). If not conducted electronically prior to visit
- Acquire clinical images, dermoscopic image, and Nevisense data for each lesion
  - Nevisense procedure: the lesion is cleansed with an alcohol wipe and the electrical impedance measurement is conducted using a spring-loaded probe and disposable electrode measuring 5mm x 5mm. The measurement takes <1 minute and the electrical impedance score (EIS) will be recorded. Larger lesions may require a second measurement at another location within the lesion.
  - Record any adverse events from the procedure
  - Neither participants nor the in-person dermatologist will be aware of the score.
- Study team will number the skin lesions using Devon Skin Marker to verify same lesion evaluated across all assessments including the in person dermatologist
- Fill out questionnaire assessing telemedicine evaluation experience so far (Supplement L)
- In-person dermatologist examination of lesion(s) using naked eye and dermoscopy
- If a biopsy is recommended by the in-person dermatologist, participant will be offered a skin biopsy procedure or offered a second appointment within 1-2 weeks for the biopsy procedure
  - If a biopsy is performed, the participant is given at-home instructions for wound care (Supplement R) and the expected wait time for the biopsy results
  - Alternatively, the participant can choose to have the procedure done at another facility. The signed ICF includes permission for the study team to obtain those medical records
  - Follow-up care to the skin biopsy will proceed per standard clinical practice and includes result communication, wound care monitoring, suture removal if applicable and recommendations for follow-up care.
- If a biopsy is not recommended by the in-person dermatologist, the participant is given the expected wait time for telemedicine recommendation phone call.

### 7.3.3 Intermediate Visits

#### Phone Call: For Participants without a Skin Biopsy recommendation by the in-person dermatologist for at least 1 lesion (Day 4+/-2)

- Communicate telemedicine recommendation (Supplement M & N)
  - If a skin biopsy is recommended, schedule participant for another in-person visit at the DCSU for skin biopsy procedure.
  - Alternatively, the participant can choose to have the procedure done at another facility. The signed ICF includes permission for the study team to obtain those medical records
  - If a skin biopsy is not recommended, thank the subject for their participation
- Administer the study completion questionnaire (Supplement L)

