#### **7.3.4 Study Completion**

Once all lesions have been evaluated, all biopsy results have been communicated, and all wounds are healing well, participants will be given a study completion questionnaire (Supplement L) regarding his/her overall experience in the study. At this point, participation in the study is complete.

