#### 10.3.3 Analysis of the Secondary Endpoint(s)

Secondary endpoint (1) will be a descriptive analysis of Sensitivity, Specificity, Positive Predictive Value, and Negative Predictive Value, using the histopathology results as the gold standard. We will assess potential difference or advantages in terms of: a) enhanced telemedicine diagnostic system; b) telemedicine Nevisense alone; c) telemedicine clinical + dermoscopy alone; and d) in-person dermatologist diagnosis. Sensitivity, Specificity, Positive Predictive Value, and Negative Predictive Value will be reported with an upper and lower confidence interval. Lesions with missing data will not be included in the relevant analyses (see Study Design schematic footnote 3). Participants lost to follow-up for reporting his/her biopsy results will be included in the analysis as the data required for analysis has been collected.

As another secondary endpoint, we will be evaluating the enhanced telemedicine service's impact on patient centered outcomes. Descriptive statistics for this secondary endpoint (2) (patient questionnaires, Supplement L will be presented as percentages. Study completion questionnaires may be qualitatively analyzed for themes and quantified by thematic representation across participants. Participant agreement of thematic categories will be calculated as percentages as a summary measure. Factors for stratification may include participants with a biopsy procedure and those without biopsy procedure as well as diagnosis of malignancy or benign lesion within those with biopsy. Participants with missing study completion questionnaire results due to inadequate duration of phone call will not be included.

As a final secondary endpoint (3), we will estimate the number of lesions that may benefit from the additional information of the Nevisense score to the clinical and dermoscopic exam. This estimation will be provided by the in-person dermatologist, and separately by each of the three teledermatologists (Supplement T & U). The estimates will be expressed as percentages. Any lesion with missing data in the in-person dermatologist and teledermatologist plan will not be included in analysis. Participants lost to follow-up will still be included in analysis of this endpoint as required data for this endpoint determination has been captured in the first visit.

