**10.3.5 Adherence and Retention Analyses**

Adherence is not applicable. Participation is defined as all subjects that enroll into the study. Study retention is defined as participants that complete all visits through the last visit (study completion questionnaire) out of the number of subjects enrolled. Participants lost to follow up include all those that were unable to be contacted for biopsy scheduling, wound check, or study completion questionnaire administration.

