**19 Supplemental Attachments**

These documents are relevant to the protocol, but they are not considered part of the protocol. They are stored and modified separately. As such, modifications to these documents do not require protocol amendments

- A. Nevisense Summary of Safety and Effectiveness (PMA)
- B. Nevisense Administration & Service Instructions
- C. Nevisense Instructions for Use
- D. Study Print Advertisement
- E. Study Online Advertisement
- F. Sample Certified Letter For Malignancy Diagnosis
- G. Sample Certified Letter For Skin Biopsy Recommendation
- H. Emergency Patient Card (samples)
- I. Nevisense Acquisition Commitment Letter from SciBase
- J. DermLite Cam Instructions for Use
- K. Enrollment Patient Questionnaire
- L. Participant Experience Questionnaires (After data acquisition, Visit 1, Visit 3)
- M. Teledermatologist Biopsy Recommendation Phone Script
- N. Teledermatologist No Biopsy Recommendation Phone Script
- O. Pre-screening Questionnaire
- P. Pre-screening and Scheduling Phone Script
- Q. Key Information Sheet (for participant)
- R. Wound Care (take-home patient sheet)
- S. Wound Care Assessment & Biopsy Result Communication Phone Script
- T. In-Person Dermatologist Data Collection Form
- U. Teledermatologist Data Collection Form

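### Section 7.3.3 puts the study completion questionnaire on the Day 4 call without condition, in conflict with 7.3.4, so some participants could answer before their biopsy or result; the timing and the response to be analysed need to be fixed.

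*Combined protocol and SAP*

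**What the plan says.** The Day 4 call in section 7.3.3 is "For Participants without a Skin Biopsy recommendation by the in-person dermatologist for at least 1 lesion (Day 4+/-2". A participant with one lesion sent for biopsy in person and another not sent therefore receives it. Its sub-items cover both outcomes of the telemedicine review. One of them is "If a skin biopsy is recommended, schedule participant for another in-person visit at the DCSU for skin biopsy procedure"; the other thanks the participant and closes. The instruction "Administer the study completion questionnaire (Supplement L" then stands as a separate item at the top level, tied to neither outcome. The later steps in 7.3.3 (Visit 2, the Day 17 call, optional Visit 3) do not mention the questionnaire.

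Section 7.3.4 sets a different trigger for the questionnaire: "Once all lesions have been evaluated, all biopsy results have been communicated, and all wounds are healing well, participants will be given a study completion".

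Two other places bear on timing. The Schedule of Events (section 20) marks the questionnaire at both the Day 4 and the Day 17 calls, each with an asterisk meaning selected participants, and does not say who is selected for which. Section 19 labels Supplement L "Participant Experience Questionnaires (After data acquisition, Visit 1, Visit 3".

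On analysis, 10.3.3 says of the satisfaction endpoint: "Factors for stratification may include participants with a biopsy procedure and those without biopsy procedure as well as diagnosis of malignancy or benign lesion", the latter among those biopsied. Section 10.3.5 states: "Study retention is defined as participants that complete all visits through the last visit (study completion questionnaire", in a parenthesis after the words for the last visit.

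**The concern.** Patient-centred outcomes are one of the study's two aims and its second secondary endpoint. If the closing questionnaire is taken on Day 4 from someone whose biopsy or pathology is still to come, the answer cannot reflect that experience. Grouping such answers by biopsy status or by malignant versus benign result then sorts people by something that had not yet happened to them, or that they did not yet know. A reader of the results could not tell those answers from ones given after the result.

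The plan also has no rule for choosing between two responses if a participant is asked on both calls. Participants whose lesions were all flagged in person get no Day 4 call, and the 7.3.3 text gives them no questionnaire contact; they depend on staff applying 7.3.4. Mistimed answers cannot be collected again, so the point is worth settling before data are gathered.

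**Working it through.** **Inputs**
- Day 4+/-2 call: Day 2-6 (7.3.3).
- Visit 2, telemedicine-recommended biopsy, Day 7+/-2: Day 5-9 (7.3.3).
- Result call for those biopsies, Day 17+/-3: Day 14-20 (7.3.3).
- Optional wound check, Day 21+/-3: Day 18-24 (7.3.3).
- Pathology turnaround: 1-2 weeks (7.2.2).
- In-person biopsy: at Visit 1 (Day 1) or at an appointment 1-2 weeks later (7.3.2).
- About 10% of participants biopsied (2.4.1), about 8% with a benign biopsy and about 2% malignant (2.4.2); enrolment target 500 (5.4, 5.6).

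**The plan's own figure.** Section 10.4 expects 50-100 biopsy recommendations and 450-900 lesions without one. 10% of 500 lesions = 50 and 10% of 1000 = 100; 90% of 500 = 450 and 90% of 1000 = 900. The figure reproduces.

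**Timing.** The gap from the Day 4 call to a later event runs from (earliest event day - 6) to (latest event day - 2).

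1. *Biopsy recommended by telemedicine.*
   - To the biopsy: 5 - 6 = -1 to 9 - 2 = 7 days. The negative end cannot occur, because the biopsy is scheduled on that call.
   - To the result call: 14 - 6 = 8 to 20 - 2 = 18 days.
   - To the wound check: 18 - 6 = 12 to 24 - 2 = 22 days.
   - A questionnaire on this call always precedes biopsy and result.
2. *One lesion flagged in person, another not.*
   - Biopsy on Day 1: result on Day 1 + 7 = 8 to 1 + 14 = 15, which is 8 - 6 = 2 to 15 - 2 = 13 days after the call.
   - Biopsy deferred 1-2 weeks: biopsy on Day 8-15 and result on Day 8 + 7 = 15 to 15 + 14 = 29, so the Day 4 answer precedes the biopsy as well.
3. *All lesions flagged in person.* No Day 4 call. The Day 17 call in 7.3.3 is headed for biopsies that followed a teledermatologist recommendation, so 7.3.3 gives this group no questionnaire contact. Section 7.3.4 does cover them.

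For groups 1 and 2, staff cannot obey both the Day 4 item and the 7.3.4 condition that "all biopsy results have been communicated, and all wounds are healing well, participants will be given a study completion questionnaire".

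**Size.** 500 x 10% = 50 biopsied; 500 x 8% = 40 benign; 500 x 2% = 10 malignant. The documents do not divide the 50 among the three groups, and group 3 cannot be asked on Day 4. So 50 and 10 are upper bounds for early answers.

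**Does the Day 17 call satisfy 7.3.4?** Not always. The wound check falls 18 - 20 = -2 to 24 - 14 = 10 days from the result call. When a wound check is held, healing may not be confirmed by the result call.

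**The case against.** The strongest reply is that the rest of the protocol points to later timing for biopsied participants. Section 7.3.4 says so directly. Section 5.5 runs participation to the end of the completion questionnaire and makes its length depend on whether a biopsy is done. The Schedule of Events carries a mark at the Day 17 result call, and its natural reading is Day 4 for those without a biopsy and Day 17 for those with one. A reader might infer from 7.3.3 that satisfaction will in fact be measured before biopsy and diagnosis. The documents do not support that as a certainty; it follows only if 7.3.3 is applied literally. What stands is that both instructions are current and the asterisk is undefined.

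A reader might also infer that retention is inflated, because someone who answers on Day 4 and never returns for the biopsy could count as complete. That is largely answered. Section 10.3.5 requires every visit to be completed, and section 15.3 treats a participant who does not follow through on a recommended biopsy as leaving before the end. What remains is the parenthesis that identifies the last visit with the questionnaire.

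It can further be said that the endpoint is satisfaction with the telemedicine evaluation, which a Day 4 answer can still measure, and that the split is optional, in a study that tests no hypotheses. This is fair and limits the harm to the split. The items asked at each time point cannot be checked, because the supplements are held outside the protocol and section 7.1.1 distinguishes a first part from a final questionnaire.

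**Conclusion.** The point holds as an unreconciled timing with a possible consequence for one descriptive secondary analysis. Followed as written, 7.3.3 would take closing answers on Day 2-6 from participants with a pending biopsy or result: 8-18 days before the result call for a telemedicine-recommended biopsy, and 2-13 days before the result for a Day 1 in-person biopsy. The optional split by biopsy and malignancy would then rest partly on strata defined by later events.

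The number affected is an unknown part of at most about 50 biopsied participants and about 10 with cancer. A reader might take this to be essentially all of both strata. The documents do not support that, because participants with every lesion flagged in person get no Day 4 call. Nor do they show that this last group will be missing, since 7.3.4 applies to them.

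The counts assume 500 participants and the participant-level rates in 2.4.1 and 2.4.2. The Protocol Summary gives 650 enrolled, which would make them 650 x 10% = 65 and 650 x 2% = 13. The primary endpoint is unaffected.

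**What to change.** - **7.3.3:** make the Day 4 item conditional. Give the questionnaire on that call only if no study lesion has a biopsy recommended or a result pending. Everyone else, including participants with all lesions flagged in person, receives it once the 7.3.4 conditions are met: at the result call, or at the wound check if one is held.
- **Section 20:** define the asterisk in the questionnaire row so that it states who is asked at which contact, and add a mark at the Day 21 contact if the wound check is used.
- **Section 19:** align the Supplement L visit labels with this rule.
- **10.3.3:** state which response is analysed if a participant has more than one.
- **10.3.5:** remove the parenthesis equating the last visit with the questionnaire, so that completion of every visit governs retention.

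The cost is protocol wording; the calls and the wound check already exist. The downside is a longer recall interval and slightly more missing questionnaires among biopsied participants.
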